1. SUMMARY

This is a 5-week, single-blinded, randomized trial to pilot test the efficacy of a behavioral intervention (CARE RA), a peer coach program, in increasing cardiovascular disease (CVD) risk assessment and self-efficacy in patients with rheumatoid arthritis (RA). Peer coaches are patients who themselves have the targeted condition (e.g., diabetes, RA) and have been trained to help others with the same condition in following treatment recommendations from their providers, social support, and improving self-efficacy, which translates into healthy behaviors. They are not physicians, nor other health professionals, and do not provide any medical advice to the patients they are coaching. We will explore their potential role to guide other patients with RA to obtain adequate CVD risk assessment, the most common cause of death in patients with RA.

The study population will consist of individuals with RA between the ages of 40-75 who have no history of established CVD and are not receiving a statin. The study duration will be 18 weeks, including a 6-week intervention period, starting from baseline enrollment and ending with the 3-month follow-up contact. Eligible subjects will be randomized to either a self-administered online learning arm or to the CARE RA arm, also called the peer coach arm. The self-administered online learning arm will include a tutorial on how to use the Patient Activated Learning System (PALS) followed by self-driven completion of the CARE RA curriculum within the PALS. The peer coach arm will include the same tutorial on the use of the PALS but will also include contacts with a peer coach for 5 weeks to reinforce key points in the CARE RA curriculum within the PALS. Each week, the peer coaches will have a 30 to 45-minute call with their assigned participant(s) during which they will discuss concepts about RA, CVD and RA, the importance of cardiovascular risk assessment, how to better communicate with your doctors, and how to request cardiovascular risk assessment from your doctor.

The primary objective is to increase the number of subjects who receive CVD risk assessment at their upcoming physician's appointment at the end of the 5-week intervention. Since some subjects might not have this test done by their physician by the end of the intervention, but may have it later on, we will also examine this outcome 3 months after the intervention is completed. We will also examine at that point if they met criteria to initiate a statin medication.

Secondary outcomes will be:

1. Change in Routine Assessment of Patient Index Data (RAPID3) score from baseline to the end of the study between arms.
2. Change in Social Support Survey Score from baseline to the end of the study between arms.
3. Change in Patient Activation Measure (PAM) score from baseline to the end of the study between arms. In order to utilize this measure, subject data will be shared with the licensing agency to help continue to improve the measure.
4. Change in Patient Health Questionnaire – 8 (PHQ-8) score from baseline to the end of the study between arms. Subjects who score a 10 or higher on the PHQ-8 at baseline data collection will be referred to mental health resources and counseling (websites, links,

educational materials) by the study team. Peer coaches will be trained to direct subjects who express depressed thoughts and feelings during the course of the program to the mental health resources and counseling and will report such instances to the research team.

5. Change in General Self-Efficacy (GSF) score from baseline to the end of the study between arms.
6. Change in Medication Understanding and Use Self-Efficacy Scale (MUSE) score from baseline to the end of the study between arms.

2. INTRODUCTION

CVD is the most common cause of death among patients with RA. Several studies showed a 50-60% increased risk of death from myocardial infarction and stroke in patients with RA compared with the general population, with the standardized mortality ratio attributable to CVD ranging from 1.13-5.15.¹⁻⁶ Aggressive treatment of RA decreases CVD morbidity and mortality, but there is evidence that many patients do not benefit from the “treat to target” paradigm and do not in fact receive sufficiently aggressive RA treatment. Thus, CVD risk assessment through cholesterol testing among patients with RA remains an important CVD risk reduction strategy.⁷⁻¹¹

Several studies have reported that the prevalence of hyperlipidemia in patients with RA is lower than in those without RA. However, the relationship between lipids, RA, and CVD risk is complicated by RA therapies that have been associated with increased lipid levels.^{12,13} We have reported previously that three different combination therapies were associated with increased lipid levels after 6 months of treatment.¹² Nevertheless, the American Heart Association/American College of Cardiology recommend following their guidelines applicable to the general population for CVD risk assessment, including cholesterol testing.

Although primary care physicians (PCPs) test RA patients’ lipids more frequently than rheumatologists, overall testing remains suboptimal, with only 44% or fewer patients with RA tested, compared with 79% of patients with diabetes mellitus (DM), another CVD risk factor that is more widely appreciated by PCPs. A significant knowledge gap has been reported among PCPs regarding RA as a CVD risk factor, with 68% of PCPs frequently failing to identify RA as a CVD risk factor,¹⁴ suggesting that specific interventions for these patients may be warranted.

One such intervention may be peer coaching. Peer coaching interventions are gaining traction for chronic disease self-care. Peer coaches have been shown to improve medication adherence for human immunodeficiency virus (HIV), asthma, diabetes, and cancer screening.¹⁵⁻²² Peer coaches are lay individuals who themselves have the targeted chronic condition and who receive minimal training. They provide social and emotional support to the patient and could be used to help patients complete an educational program that includes decision support for CVD risk reduction strategies. However, peer coaches have not been used in RA, and have not been evaluated for CVD risk reduction in this population. Volunteer peer coaching programs are especially attractive in the context of patient communities, such as the online research community of >28,000 patients with arthritis enrolled in ArthritisPower. In preliminary discussions with my patients, several expressed interest in having contact with someone also living with arthritis to guide them through an educational program on CVD risk, ultimately helping them to discuss CVD risk reduction with their physician.

This study will use Bandura's Social Cognitive Theory to develop an online CVD risk reduction intervention for patients with RA. This theory proposed that experiential learning helps people to overcome their fears and impediments and can serve as a facilitator for behavioral change. Social support is also very important and can be achieved by interacting with others who have had similar experiences.

3. STUDY OBJECTIVES AND OUTCOMES

3.1 Primary Objective

The primary objective is to test the difference in the proportion of subjects who receive cardiovascular risk assessment or learning from their healthcare provider that they already had one in the past year, between subjects randomized to the peer coaching condition and subjects randomized to the self-administered online learning condition.

3.2 Secondary objectives:

To determine whether the CARE RA program is effective in improving the following patient generated health data compared to subjects in the self-administered online learning arm.

1. Change in Routine Assessment of Patient Index Data (RAPID3) score from baseline to the end of the study between arms.
2. Change in Social Support Survey Score from baseline to the end of the study between arms.
3. Change in Patient Activation Measure (PAM) score from baseline to the end of the study between arms.
4. Change in Patient Health Questionnaire – 8 (PHQ-8) score from baseline to the end of the study between arms. Subjects who score a 10 or higher on the PHQ-8 at baseline data collection will be referred to mental health resources and counseling (websites, links, educational materials) by the study team. Peer coaches will be trained to direct subjects who express depressed thoughts and feelings during the course of the program to the mental health resources and counseling and will report such instances to the research team.
5. Change in General Self-Efficacy (GSF) score from baseline to the end of the study between arms.
6. Change in Medication Understanding and Use Self-Efficacy Scale (MUSE) score from baseline to the end of the study between arms.
7. We will examine the feasibility of the intervention by having 80% or more of the subjects complete the intervention.

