8. ANALYSIS AND STATISTICS

8.1 Power Calculations and Sample Size

The primary outcome measure is the percentage of patients in each arm that had a lipid panel checked or initiated LLT. Assuming 80% of the subjects in the intervention group have their lipids checked within the 3 months of the study, and 60% of the subjects in the control group have their lipid checked N=64 subjects per group would have at least 80% power to detect a margin difference of 20%, for a one-sided test and significance level of 0.05. We recognize that the sample of 128 subjects is modest, which reflects the pilot nature of the study in the context of a training grant. We will use data from this pilot study to design a more definitive trial powered to detect smaller differences in the primary outcome, and to compare usual care with the intervention.

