8.2 Data Analysis

To analyze the data, descriptive analyses (means, medians, standard deviations, proportions, and frequency distributions) and correlation analyses (Spearman/Pearson rank correlations) will be conducted to assess and describe the cohort. Baseline comparability between study arms will be assessed with parametric and nonparametric analyses including two sample t-tests, Wilcoxon Rank Sum, and Chi-Square tests of proportions. Every effort will be made to keep subjects in the study for the entire follow-up. Analysis will be based on intention-to-treat, regardless of whether the subject completed the intervention program. The primary outcome is the percentage of patients with lipids checked (available now through national laboratory chain) or that reported having their lipids checked. Secondary outcomes include the percentage of subjects that reported initiating LLT, self-efficacy, and patient activation as described above. We will determine these outcomes in each group (self-administered online learning program and the CARE RA arm) as well as differences in these outcomes between the groups. Two-sided t-tests will be used to calculate differences and P values ≤ 0.05 will be considered statistically significant. We will examine differences in socio-demographics, disease severity, and depressive symptoms. These characteristics will be included in a multivariable logistic regression model to determine their association with the outcome (lipids being checked) and potentially increase the statistical power of the test of group differences.

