	
 -How many subjects in the CARE RA arm received a cholesterol test during the program compared to the control arm? -How many subjects in the CARE RA arm received a cholesterol test by 1-week post intervention follow up compared to the control arm? -How many subjects in the CARE RA arm received a cholesterol test by 3-months post intervention follow up compared to the control arm? -How many subjects in the CARE RA arm initiated a statin, if indicated, after completion of the program in each arm? - See statistical analysis section for details. -How many subjects saw an improvement in their secondary outcomes (RAPID3, SSS, PHQ-8, PAM, MUSE, and GSE) from baseline to 1-week and 3-month post intervention data collection between arms? -Were you able to understand the program information? -Do you believe the program information is valuable to living a healthy life?
ADOPTION	Organization Level
	
 -What factors contributed to ArthritisPower and its members, and the Bendcare network, to taking up the intervention? -What barriers interacted with the intervention to prevent adoption within ArthritisPower and the Bendcare patient network? 
ADOPTION will be assessed upon completion of the trial through talking with members of the ArthritisPower community and the Bendcare patient network.

IMPLEMENTATION **Individual Level**

- To what extent were the intervention components delivered as intended in the protocol?
- How was the intervention implemented? By whom and when?
- How was the program adapted or modified over time?
- What was it like to deliver this program to individuals with rheumatoid arthritis?
- What do you think was most successful? What were the major barriers in implementing this program?
- What was it like to conduct the weekly sessions?
- Would you do anything to revise the program?
- Does the program improve my ability to deal with life's challenges to my health?
- Does using the program makes it easier to live a healthier life?
- Is the program useful in my life?
- How satisfied are you with the program?
- Was participating in the program difficult for you?
- Would you recommend the program to people you know?

This dimension will be assessed through surveys and focus groups/interviews with the subjects.

MAINTENANCE **Organizational and Individual Level**

- What was the attrition rate; were drop-outs representative of the target population?

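### The primary outcome has no single definition: event and time point differ between the Summary and sections 3.1, 8.1 and 8.2, and the stated power fits only one of the combinations

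*Combined protocol and SAP*

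**What the plan says.** Four places in the combined protocol and SAP define the primary outcome.

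- **Summary (section 1).** The event is a CVD risk assessment received at the physician "appointment at the end of the 5-week intervention". The later look is additional: "we will also examine this outcome 3 months after the intervention is completed".
- **Section 3.1.** Success is to "receive cardiovascular risk assessment or learning from their healthcare provider that they already had one in the past year". No time point is given.
- **Section 8.1.** "The primary outcome measure is the percentage of patients in each arm that had a lipid panel checked or initiated LLT". The planning rates, however, concern lipid checks alone: "Assuming 80% of the subjects in the intervention group have their lipids checked within the 3 months of the study", against 60% in the control group. With 64 per group, the section claims at least 80% power, one-sided at 0.05.
- **Section 8.2.** "The primary outcome is the percentage of patients with lipids checked (available now through national laboratory chain) or that reported having their lipids checked". LLT is placed elsewhere: "Secondary outcomes include the percentage of subjects that reported initiating LLT". No time point is given.

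Table 4 in section 9 asks about testing over three windows: during the program, by one week after it ("received a cholesterol test by 1-week post intervention follow up compared to the control arm") and by three months after it. It points to the statistical section for details, and that section does not say which window is primary.

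Section 5.2 caps participation at 18 weeks. Section 5.1 does not exclude people with a recent lipid test. Table 2 and sections 7.4 and 7.10 list two outcome items, the cholesterol test and the start of LLT. The baseline items in Table 2 and section 7.3 name no earlier lipid test.

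**The concern.** Both the event and the window change with the section followed. LLT is an alternative component of the primary outcome in 8.1 and a secondary outcome in 8.2. The Summary ranks the end of the intervention first, while 8.1 ties its rates to three months without saying from when.

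The past-year clause is the most consequential difference. Follow-up lasts at most 18 weeks, so an assessment from the past year can predate randomisation. Under 3.1 it becomes a success once the subject hears of it. Coaching on how to talk with physicians could change who hears of it, so the arm difference may reflect new testing, new awareness of old testing, or both. The documents do not show how the two are told apart.

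At stake are the meaning of the primary comparison, the freedom to choose a definition after seeing the data, and the event rates that would be carried into the larger trial this pilot is meant to inform.

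**Working it through.** **1. The passages side by side**

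| Place | Event | LLT counts? | Learning of a past-year assessment counts? | Time point |
|---|---|---|---|---|
| Summary | CVD risk assessment | no | not stated | end of 5-week intervention; 3 months also examined |
| 3.1 | CVD risk assessment | no | yes | none |
| 8.1, definition | lipid panel | yes | not stated | none |
| 8.1, rates | lipids checked | no | not stated | 3 months, start not stated |
| 8.2 | lipids checked (laboratory or self-report) | no, secondary | not stated | none |

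The Introduction treats cholesterol testing as the means of CVD risk assessment, which narrows the gap in the event wording. It explains neither LLT, nor the past-year clause, nor the windows.

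**2. The plan's own figure**

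Inputs from 8.1: p1 = 0.80, p2 = 0.60, one-sided alpha 0.05, power 0.80. The mean proportion is 0.70.

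n = [1.645·√(2·0.70·0.30) + 0.842·√(0.80·0.20 + 0.60·0.40)]² / 0.20² = (1.066 + 0.532)² / 0.04 = 63.9, so 64 per group.

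The normal approximation gives 80.1% power at 64 per group. Exact enumeration of both binomials with the pooled z-test gives 80.7%. The stated sample size is therefore correct for lipids checked within three months.

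**3. What the past-year clause could do (illustration)**

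Let q be the share of each arm tested in the past year. The documents give no value, so q is assumed, and the 80% and 60% rates are applied to the remaining subjects.

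- All of q count as events: p = q + (1−q)·0.80 versus q + (1−q)·0.60.
- None of q count and none are retested: p = (1−q)·0.80 versus (1−q)·0.60.

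In both cases the arm difference is 20·(1−q) points. Power is exact, one-sided 0.05, 64 per arm.

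| q | Difference | All of q count | None of q count |
|---|---|---|---|
| 0 | 20 points | 80% vs 60%: 80.7% | same |
| 10% | 18 points | 82% vs 64%: 75% | 72% vs 54%: 69% |
| 20% | 16 points | 84% vs 68%: 69% | 64% vs 48%: 56% |
| 30% | 14 points | 86% vs 72%: 63% | 56% vs 42%: 46% |

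If learning differs by arm, the success rate in an arm is q times the share who learn, plus (1−q) times its testing rate. At q = 20%:

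- 100% learn in CARE RA and 60% in control: 0.20 + 0.64 = 84% versus 0.12 + 0.48 = 60%, power 93%.
- The reverse: 0.12 + 0.64 = 76% versus 0.20 + 0.48 = 68%, power 26%.

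**4. What the window could do (illustration)**

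Suppose only 90%, 80% or 70% of the three-month tests are done by the end-of-intervention contact, equally in both arms (again an assumption). The proportions are then 72% vs 54%, 64% vs 48% and 56% vs 42%. These are the pairs in the last column above, with power 69%, 56% and 46%.

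The documents give no basis for a figure on LLT.

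**The case against.** The best defence is that all four places mean a cholesterol test, loosely worded, in a declared pilot. Part of this stands. The Introduction supports reading risk assessment as cholesterol testing. LLT may add few events, because statin users are excluded and the sessions treat statin initiation as a step after the test. The power illustrations rest on extreme cases, such as everyone learning or nobody being retested, and there is no loss at all if 60% and 80% already describe the chosen event in the enrolled population. The pilot label does not settle the matter, since the plan sets a primary comparison with a stated power.

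A reader might infer more than the documents support:

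- **That the trial is underpowered or the sample size is wrong.** The figure of 64 reproduces; what is unclear is which event and window it serves. Section 8.2 does use two-sided tests where 8.1 is one-sided (exact power at two-sided 0.05 is about 71%), but that is a separate point.
- **That the past-year clause favours CARE RA.** The direction is unknown, as the 93% and 26% cases show.
- **That three months is the natural primary time point.** The only explicit ranking is in the Summary, and it puts the end of the intervention first. The three months in 8.1 belong to a rate assumption, not to the outcome definition.
- **That new and earlier tests cannot be separated.** The documents list headings, not the full REDCap forms, and the laboratory records in 8.2 may date some tests. What can be said is that no method of separation is shown.

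**Conclusion.** The point holds as an internal contradiction and should be corrected before analysis. The LLT conflict between 8.1 and 8.2, the different windows in the Summary and 8.1, and the past-year clause found only in 3.1 can all be read directly from the text and need no assumption. The stated power of at least 80% applies to lipids checked within three months, and nothing shows that it carries over to the other definitions.

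The size of the effect is not known. Under the assumed q of 10–30%, power is 75–63% with the clause fully counted and 69–46% with none of q counted. With unequal learning at q = 20% it is 93% or 26%, depending on direction. These figures show how much the choice of definition can matter; they are not forecasts.

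The timing of the early outcome call relative to the appointment, and the anchor of the three-month follow-up in 5.2, are separate scheduling points to be reconciled in their own right.

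**What to change.** 1. **One event, one time point.** State both before analysis and use them identically in the Summary, 3.1, 8.1 and 8.2. Remove LLT initiation from the 8.1 primary outcome, as 8.2 already does. The sponsor chooses between the end-of-intervention contact, which the Summary ranks first, and the three-month contact, which matches the rate window in 8.1. Report the other as secondary.
2. **Past-year clause.** State whether it is part of the primary outcome. At each outcome contact, record the test date, or whether the event is a new test or learning of an earlier one. Report the two separately by arm, and prespecify the other definition as a sensitivity analysis.
3. **Power.** Confirm that 60% and 80% describe the chosen event and window, or restate the power.

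Testing in the past year should not be required as a covariate in the 8.2 logistic model. Subjects unaware of a test cannot report it. Under section 5.4 the baseline form is completed after the arm has been disclosed. If the clause is kept, the covariate could also predict the outcome completely.

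The cost is protocol and SAP wording, one item at each outcome contact and one sensitivity analysis, with no extra subjects or visits. The trade-off is that the stated power may look less favourable once the rates are tied to one event and window.

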4. STUDY DESIGN

[figure not shown]
4.1 Study description

This is a single-blinded randomized trial to pilot test the effectiveness of the CARE RA intervention with self-administered online learning. The CARE RA intervention consists of 3 components: peer

support, patient activation, and online education via the PALS (Figure 1). It consists of weekly one-on-one telephonic sessions with a peer coach (a person with RA who has been trained on delivering the content of the CARE RA intervention to another person with RA) for five weeks. The intervention will begin at least 6 weeks before the subject's next appointment with a rheumatologist or other physician on their care team. During the intervention, subjects will learn how RA can affect their heart and receive training on how to better communicate with their physician so that they can obtain appropriate CVD risk assessment.

The peer coaches will be recruited and trained before deployment of the intervention. The recruitment and training of peer coaches for the CARE RA program is described below.

Figure 1: Components of the CARE RA Intervention

